### 3 OBJECTIVES AND ENDPOINTS

OBJECTIVES	ENDPOINTS	JUSTIFICATION FOR ENDPOINTS
Primary		
To assess the efficacy of immersive Skills-Based VR and Distraction VR in improving perceived pain from baseline to Day 30. The trial will be considered a success if there is statistical evidence of improvement in either VR group compared to sham VR.	The change from study baseline to Day 30 in pain interference as measured by the 8-item PROMIS Pain Interference scale is the primary endpoint. This scale measures the consequences of pain on relevant aspects of life, including the extent to which pain hinders engagement with social, cognitive, emotional, physical, and recreational activities.  The study will be considered a success if there is a statistically significant difference of 5 points in the Pain Interference score between participants in either the Skills-Based or Distraction VR arm compared with the Sham VR arm.	The NIH Pain Consortium Research Task Force (RTF) draft standards for research on cLBP recommend a uniform minimal data set that includes self-reported measures of pain interference.   The PROMIS PI scale is a validated instrument with excellent content validity, construct validity, and reliability in patients with chronic pain. Past work indicates that changes of 3.5 to 5.5 points in PROMIS-PI scores of people with LBP can be considered meaningful. 
Secondary		

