## 9.2 SAMPLE SIZE DETERMINATION

### Sample Size calculations

The primary goal of this aim is to test the efficacy of immersive VR in improving perceived pain. The trial will be a success if there is statistical evidence that either immersive VR group is better than control or sham VR. Preliminary studies showed that the PROMIS pain interference scale has a SD of 10. Assuming that the SD at baseline ( $SD_0$ ) and at 30 days ( $SD_1$ ) are similar and equal to 10 for this population, the variance for the difference in PROMIS from baseline to 30 days after intervention is  $Var_{diff} = SD_0^2 + SD_1^2 - 2\rho SD_0 SD_1$ , where  $\rho$  is the correlation coefficient between measurements at baseline and 30 days. A conservative estimate of this variance is achieved when  $\rho = 0$ . Therefore, the estimate  $SD_{diff} = (10^2 + 10^2)^{0.5} = 14.14$ . Let  $m_c$ ,  $mv_1$ , and  $mv_2$  be the mean change in PROMIS score from baseline to 30 days for the control, VR1, and VR2 groups, respectively.

We estimate power by simulating 10000 trial replicates and testing the null hypothesis that  $H_0: m_c = mv_1 = mv_2$  versus the alternative hypothesis that  $H_1: m_c \neq mv_1$  or  $m_c \neq mv_2$ . To maintain the familywise error rate at 0.05, a two-sample t-test is used to compare the control arm to each VR arm and the test is declared statistically significant if the p-value of the two-sided test is less than 0.025. Under the alternative hypothesis that  $|m_c - mv_1| = |m_c - mv_2| = 5$ , data from 120 patients in each of the three arms achieve 83% power to detect a clinically meaningful effect 5 units in the PROMIS score. The actual type I error rate is 0.049. For the secondary outcome of comparison between the two VR arms, we test the null hypothesis that  $H_0: mv_1 = mv_2$  versus the alternative hypothesis that  $H_1: mv_1 \neq mv_2$  at the two-sided 0.05 level of significance if there is statistical evidence that both VR arms are better than control. Using the same assumptions as above and simulating 10000 trial replicates, then if both VR arms are better than the control arm, we can achieve 71.4% power to detect 5 units in PROMIS score between the two VR arms. This power was derived under the alternative hypothesis  $|m_c - mv_1| = 5$  and  $|mv_1 - mv_2| = 5$ . The actual type I error rate for this conditional test is 0.02.

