#### 9.4.2 ANALYSIS OF THE PRIMARY EFFICACY ENDPOINT(S)

The goal of this analysis is to test the effectiveness of immersive VR in improving measures of pain interference. The trial will be a success if there is statistical evidence that either immersive VR group is better than sham VR.

The primary efficacy endpoint is the change from study baseline to Day 30 in pain interference as measured by PROMIS-PI t-score. The primary analysis will compare each treatment group separately to the control group using a linear mixed model repeated measures (MMRM) analysis. The repeated measures are the change from baseline PROMIS-PI t-score obtained at Days 7, 15, and 21, respectively. The model will include fixed categorical effects for treatment, week, treatment by week interaction, and the baseline PROMIS-PI t-score as a continuous covariate. We will employ the Stata *xtmixed* command

with restricted maximum likelihood estimation (REML) and an unstructured within-patient covariance structure for this model. We will evaluate the assumptions of the model, including normality, using residual and other diagnostic plots of model fit.

From this model, we will estimate least squares means, standard errors, treatment differences in least squares means, and 95% confidence intervals for each time period. Primary inference will be based on the treatment comparison of least squares means for Day 30, and a p-value will be presented for this time period only. The null hypothesis is that the mean difference in the primary endpoint between the treatment groups and the sham control group is zero, versus the alternative hypothesis that these differences are not zero. The hypotheses can be expressed as follows:

$$H0_a: \mu_{SB} - \mu_{control} = 0 \text{ versus } H1_a: \mu_{SB} - \mu_{control} \neq 0$$

$$H0_b: \mu_D - \mu_{control} = 0 \text{ versus } H1_b: \mu_D - \mu_{control} \neq 0$$

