Where  $\mu_{SB}$  refers to the mean change from baseline to Day 30 in Promis-PI t-score in the Skills-based VR treatment group,  $\mu_{control}$  refers to the mean change from baseline to Visit Day 30 in Promis-PI t-score in the sham treatment group, and  $\mu_D$  refers to the mean change from baseline to Day 30 in Promis-PI t-score in the Distraction VR treatment group. The test will be performed using the final MMRM model with a two-sided significance level of 5%. Estimated least squares means for change from baseline and the observed absolute values ( $\pm$  SE) by treatment group will be plotted over time.

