#### 3.5.1 Power Estimation

For the primary endpoint of the study, there is 83% power to detect a clinically meaningful effect size of 5 units in PROMIS score between control and either VR arms at the 0.05 level of significance. This requires 360 patients randomized on a 1:1:1 ratio.

For one of the secondary endpoints of comparison between the two VR arms, we test the null hypothesis that  $H_0: mv1 = mv2$  versus the alternative hypothesis that  $H_1: mv1 \neq mv2$  at the two-sided 0.05 level of significance if there is statistical evidence that both VR arms are better than control. Using the same assumptions as above and simulating 10000 trial replicates, then if both VR arms are better than the control arm, we can achieve 71.4% power to detect 5 units in PROMIS score between the two VR arms. This power was derived under the alternative hypothesis  $|mc - mv1| = 5$  and  $|mv1 - mv2| = 5$ . The actual type I error rate for this conditional test is 0.02.

For assessing the effect of VR on treatment response, we estimate power using a logistic regression model, accounting for all possible confounding factors as described in the protocol.

The outcome variable is treatment response (binary) and the predictor of interest is VR type, Distraction versus Skills-based. Table 1 gives the minimum odds ratio that can be detected with 80% power with the two-sided 0.05 level of significance as a function of baseline probability of positive response when a patient is treated with traditional VR and  $R^2$ , the proportion of variability in the predictor of interest (VR type) that is explained by all relevant baseline covariates in the model using data from 120 patients in the Distraction VR arm and 120 in the Skill-based VR arm. For example, data from 240 patients achieve 80% power to detect an odds ratio of 2.19 if the probability of positive response when a patient is treated with Distraction VR is 0.3 and 10% of the variability in VR type is explained by all other baseline covariates in the model. These odds ratios vary between 2.01 and 2.8 and are clinically meaningful. Therefore, we have enough power to test statistical significance of predictors of interest in the multivariable logistic regression model.

**Table 1.** Minimum detectable odds ratio as a function of the proportion of variability in VR type variable that is explained by all other relevant covariates in the model and the baseline probability of positive treatment response.

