### **6.3 Multiple Comparisons/Multiplicity**

The family-wise type I error rate (FWER) for the statistical tests of the primary and secondary endpoints will be controlled at 0.05. To strongly control the FWER at this level, a gate-keeping approach will be utilized in which each family of statistical tests will be conducted in a sequential manner. A closed testing procedure will be employed to control the FWER. Hypothesis tests conducted for exploratory purposes will be conducted outside of any gatekeeping.

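### The primary analysis sections give an unsplit two-sided 5% for two Day 30 comparisons, omit the p<0.025 used for planning, and SAP 6.3 does not name the closed test that would settle the rule

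*Protocol*

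**What the plan says.** **Planning sections.** Protocol 9.2 and SAP 3.5 compare each VR arm with sham by a two-sample t-test, and "the test is declared statistically significant if the p-value of the two-sided test is less than 0.025". Both give the purpose: a familywise error rate of 0.05.

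**Analysis sections.** Protocol 9.4.2 and SAP 4.6.1 set out one null hypothesis for Skills-based VR and one for Distraction VR. Success is disjunctive: "The trial will be a success if there is statistical evidence that either immersive VR group is better than sham VR". The level follows: "The test will be performed using the final MMRM model with a two-sided significance level of 5" percent. Neither section mentions 0.025, a split, or SAP 6.3. The general default in protocol 9.4.1 and SAP 4.1 is also two-sided 0.05 unless something else is stated.

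**Power summary.** SAP 3.5.1 repeats the 83% power for 5 points "between control and either VR arms at the 0.05 level of significance".

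**Multiplicity section.** SAP 6.3 says: "The family-wise type I error rate (FWER) for the statistical tests of the primary and secondary endpoints will be controlled at 0.05". It adds sequential gatekeeping between families of tests, and "A closed testing procedure will be employed to control the FWER". It does not list the families, name the local tests, or give a level for the two arm comparisons.

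**Success wording.** Protocol section 3 and the SAP objectives table also describe success as "a statistically significant difference of 5 points in the Pain Interference score between participants" in either VR arm and those in the sham arm.

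**The concern.** The sections from which the primary test would be programmed do not carry the threshold on which the trial was sized. Under an either-arm rule the per-comparison level decides whether the trial is declared positive. If the smaller of the two p-values were 0.03, the trial would fail under protocol 9.2 and SAP 3.5 and succeed on the literal wording of protocol 9.4.2 and SAP 4.6.1. SAP 6.3 should decide between them but only promises control. Several closed tests fit its wording and do not always give the same decision. Leaving the choice open until results are seen puts the headline conclusion at risk of a post hoc decision.

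**Working it through.** **Inputs** (protocol 9.2, SAP 3.5): 120 per arm, 1:1:1; SD 10 at baseline and at Day 30; correlation ρ = 0 between them; true difference 5 points in both VR arms. The two test statistics share the sham arm, so with equal arms their correlation is 0.5.

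**1. Reproduce the plan's figures (change-score t-test).**
- SD of change = √(10² + 10²) = 14.14
- SE = 14.14 × √(2/120) = 1.826
- Non-centrality = 5 / 1.826 = 2.74

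Familywise error is from the bivariate normal (critical values 2.241 and 1.960). Power is from simulated t-tests with 238 df.

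| Quantity | p<0.025 each | p<0.05 each | Stated |
|---|---|---|---|
| Familywise error, two-sided | 4.65% | 9.07% | 0.049 |
| Familywise error, wins favouring VR only | 2.32% | 4.54% | – |
| Power, at least one arm | 83% | 90% | 83% |

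The stated 83% belongs to 0.025 per comparison. The stated 0.049 is compatible with 0.0465: with 10,000 replicates the Monte Carlo SE is √(0.0465 × 0.9535 / 10,000) = 0.0021, so the gap of 0.0025 is about 1.2 SE. It is not compatible with 0.091.

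**2. Which rule did the planning use?** The plan says of Skills-based versus Distraction VR that "we can achieve 71.4% power to detect 5 units in PROMIS score between the two VR arms", with a conditional type I error of 0.02. I tested the two VR arms against each other at 0.05, given that both had beaten sham.

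| | Flat 0.025 | Holm | Stated |
|---|---|---|---|
| Power (differences from sham 5 and 10) | 71% | 73% | 71.4% |
| Error (differences 5 and 5) | 0.021 | 0.026 | 0.02 |

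Flat 0.025 fits, so the planning rule can be identified from the plan's own numbers.

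**3. How far closed tests differ.** At 5 points in both arms, either-arm power is 83% for flat 0.025 and for Holm, and 84% for Hochberg. Both-arm power is about 54% for flat 0.025 and 65% for Holm. A Dunnett-type test would need about 0.027 for the smaller p.

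**4. Size of the disputed zone (smaller p between 0.025 and 0.05).** The t critical values with 238 df are 1.970 and 2.256.
- *Planning t-test:* 1.970 × 1.826 = 3.60 and 2.256 × 1.826 = 4.12 points. Probability 90.0% − 83.3% = 6.7%.
- *Planned model:* protocol 9.4.2 and SAP 4.6.1 adjust for baseline. The residual SD is 10 × √(1 − ρ²), which is 10 at ρ = 0. SE = 10 × √(2/120) = 1.291. The zone is 1.970 × 1.291 = 2.54 to 2.256 × 1.291 = 2.91 points. Either-arm power is 98.7% at 0.025 and 99.4% at 0.05, so the probability is about 0.8%. At ρ = 0.5 the residual SD is 8.66 and the probability about 0.1%. This treats the Day 30 contrast as a baseline-adjusted comparison with complete data.
- *No true effect in either arm:* 9.07% − 4.65% = 4.4%, whatever the SD.

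**The case against.** The strongest reply is that the documents can be harmonised. Protocol 9.2 and SAP 3.5 tie 0.025 explicitly to a familywise 0.05, so the 5% in the analysis sections and the 0.05 in SAP 3.5.1 may simply be that familywise level. SAP 6.3 supports this reading. It is plausible, but it is inference: neither protocol 9.4.2 nor SAP 4.6.1 calls its 5% an overall level, and even on that reading the per-comparison level is missing where the test is specified.

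A reader might infer that the trial plans two unadjusted 5% tests and so runs a familywise error of about 9.1%. The documents do not support that. SAP 6.3 promises strong control at 0.05, which excludes that reading; what it leaves open is which closed test applies. Nor does the wording about sequential testing settle this, because it orders families of tests and not the two arms.

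A reader might also take the zone of 3.6 to 4.1 points and the 6.7% as properties of the planned analysis. They belong to the planning t-test. Under the baseline-adjusted model the zone is lower and, at a 5-point effect, rarely entered.

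Finally, if the 5-point success wording requires an observed difference of 5 points, a result in the zone fails under both thresholds and no success decision changes. Protocol 9.4.2 and SAP 4.6.1 state success without that condition, so this limits the consequence but does not settle the rule.

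**Conclusion.** The inconsistency stands in the current text of both documents and concerns the success rule for the primary endpoint. The analysis sections omit the planned p<0.025 per comparison, SAP 3.5.1 attaches the 83% power to a level at which the power would be 90%, and SAP 6.3 commits to control without giving the operative rule.

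The practical size is modest. Among the closed tests considered, either-arm power differs by about one percentage point. The chance of landing in the disputed zone at a 5-point effect in both arms is about 6.7% for the planning t-test and about 0.8% or less for the planned model, on the assumptions of SD 10, ρ of at least 0 and complete Day 30 data. Missing data or smaller true effects can make it larger; with no effect in either arm it is 4.4%. Because the rule decides the trial's headline conclusion and costs almost nothing to state, it should be settled before the Day 30 comparison is run.

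**What to change.** 1. In protocol 9.4.2 and SAP 4.6.1, replace the 5% level with: *Each VR arm versus sham at Day 30 is tested at two-sided p<0.025 (familywise 0.05).*
2. In SAP 6.3, name this rule for the primary family. It is a valid, conservative closed test and restores the rule used for planning.
3. In SAP 3.5.1, change the level attached to the 83% power to: *at 0.025 per comparison (familywise 0.05).*
4. Reconcile the condition for the VR-versus-VR test. Protocol 9.2, SAP 3.5 and SAP 3.5.1 condition it on both VR arms beating sham; protocol 9.1 opens it on Skills-based versus sham alone. The 71.4% and 0.02 apply only to the former.

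Holm is an acceptable alternative: the smaller p is tested at 0.025 and, if significant, the other at 0.05. Either-arm power stays at 83% and both-arm power rises from about 54% to 65%. If it is chosen, the flat 0.025 in protocol 9.2 and SAP 3.5 must also change, and the VR-versus-VR figures there and in SAP 3.5.1 become about 73% and 0.026.

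Cost: the threshold fix (items 1 to 3) takes one sentence in each of three sections and one phrase in a fourth, with no change to data or sample size. The downside is that a lone p-value between 0.025 and 0.05 does not count as success, which the sample size already assumed.

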#### 9.4.3 ANALYSIS OF THE SECONDARY ENDPOINT(S)

##### *PROMIS-Pain Interference*

The change from study baseline to Day 60 and 90 in pain interference as measured by PROMIS-Pain Interference is a secondary endpoint. This analysis will compare the treatment groups, separately, to the control group using a MMRM analysis. The repeated measures are the change from baseline PROMIS-Pain Interference score obtained for Day 60 and 90, respectively. The model will include fixed categorical effects for treatment, week, treatment by week interaction, and the baseline PROMIS-Pain Interference score as a continuous covariate. We will employ the Stata *xtmixed* command with REML and an unstructured within-patient covariance structure for this model. We will evaluate the assumptions of the model, including normality, using residual and other diagnostic plots of model fit.

From this model, we will estimate least squares means, standard errors, treatment differences in least squares means, and 95% confidence intervals for each time point. Primary inference will be based on the treatment comparison of least squares means for Day 90, and a p-value will be presented for this time period only. The null hypothesis is that the mean difference in the primary endpoint between the experimental arms and the sham arm is zero, versus the alternative hypothesis that this difference is not zero.

##### *PROMIS-Sleep Disturbance*

The change from study baseline to Day 90 in sleep disturbance as measured by PROMIS-Sleep Disturbance is a secondary endpoint. This analysis will compare the treatment groups, separately, to the control group using a MMRM analysis. The repeated measures are the change from baseline PROMIS-Sleep Disturbance score obtained at Days 15, 30, 60, and 90, respectively. The model will include fixed categorical effects for treatment, week, treatment by week interaction, and the baseline PROMIS-Sleep Disturbance score as a continuous covariate. We will employ the Stata *xtmixed* command with REML and an unstructured within-patient covariance structure for this model. We will evaluate the assumptions of this model, including normality, using residual and other diagnostic plots of model fit.

From this model, we will estimate least squares means, standard errors, treatment differences in least squares means, and 95% confidence intervals for each time point. Primary inference will be based on the treatment comparison of least squares means for Day 90 from this model, and a p-value will be presented for this time period only. The null hypothesis is that the mean difference in the primary endpoint between the experimental arms and the sham arm is zero, versus the alternative hypothesis that this difference is not zero.

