## 1.2 SCHEMA

### 1.3 SCHEDULE OF ACTIVITIES (SOA)

Procedures	Pre-screening	Screening Week Day -8 to -2	Enrollment Day -1 to 0	Day 1 (+ 6 days)	Day 7 (+ 6 days)	Day 15 (+ 6 days)	Day 21 (+ 6 days)	Day 30 (+ 6 days)	Day 45 (+ 6 days)	Day 60 (+ 6 days)	Day 75 (+ 6 days)	Day 90 (+ 6 days)
Prospective patient identified (DEEP 6 or provider registry)	X											
Confirm eligibility and Informed Consent via telephone and REDCap	X											
Online Pain Intensity Journal (7 days)		X										X
Screening Week Online Baseline Survey (see below)		X										
Randomization			X									
Participant receives study intervention kit			X									
Technical onboarding call				X								
Intervention: Participant uses VR therapy program and wears Fitbit Charge 4 watch				X	-----							X
Online survey: NIH HEAL Minimum Dataset	X											X
Immersive Tendency Questionnaire (ITQ)  and Motion Sickness Propensity Survey 	X											
Treatment expectation question	X											
Simulator Sickness Questionnaire (SSQ)  and Presence Survey				X								
Online survey: Primary outcome: PROMIS® Pain Interference	X			X	X	X	X	X	X	X	X	X
Discontinuation of Treatment Questionnaire				X	X	X	X	X	X	X	X	X
PROMIS® Physical Function  , Anxiety  , Depression  , Sleep disturbance  ; Pain intensity/interference with Enjoyment of life/interference with General activity (PEG)  , PCS-6 	X				X		X	X		X	X	X
EMR data: Charlson Comorbidity Index  , CURES and EMR: Prescription Data	X											X
Perceived study arm question, treatments in the last 90 days question												X
Online survey: PHQ-2, GAD-2, PGIC, TAPS [1/2]	X											X
Remote technical support				X	-----							X
End of study procedure question												X

Procedures	Pre-screening	Screening Week Day -8 to -2	Enrollment Day -1 to 0	Day 1 (+ 6 days)	Day 7 (+ 6 days)	Day 15 (+ 6 days)	Day 21 (+ 6 days)	Day 30 (+ 6 days)	Day 45 (+ 6 days)	Day 60 (+ 6 days)	Day 75 (+ 6 days)	Day 90 (+ 6 days)
Event Assessment: AE, SAE and UP review and reporting				X	X	X	X	X	X	X	X	X

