#### *PROMIS-Anxiety*

The analysis approach for this endpoint mirrors the above description for PROMIS-Anxiety

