#### *PCS SF-6*

The change from study baseline to Day 90 in pain catastrophizing as measured by PCS SF-6 is a secondary endpoint. This analysis will compare the treatment groups, separately, to the control group using a MMRM analysis. The repeated measures are the change from baseline PCS SF-6 score obtained for Day 15, 30, 60, and 90, respectively. The model will include fixed categorical effects for treatment, week, treatment by week interaction, and the baseline PCS SF-6 score as a continuous covariate. We will employ the Stata *xtmixed* command with REML and an unstructured within-patient covariance structure for this model. We will evaluate the assumptions of this model, including normality, using residual and other diagnostic plots of model fit.

From this model, we will estimate least squares means, standard errors, treatment differences in least squares means, and 95% confidence intervals for each time point. Primary inference will be based on the treatment comparison of least squares means for Day 90 from this model, and a p-value will be presented for this time period only. The null hypothesis is that the mean difference in the primary endpoint between the experimental arms and the sham arm is zero, versus the alternative hypothesis that this difference is not zero.

The change from study baseline to Day 90 in weekly MME of prescribed medication is a secondary endpoint. Descriptive summary statistics will be presented for weekly MME of prescribed medication at two timepoints: baseline and Day 90. Analysis of this endpoint will compare the difference in weekly MME of prescribed medication between the treatment groups and control group at baseline and Day 90 using analysis of covariance (ANCOVA), adjusting for baseline MME. We will assess the assumptions underpinning the ANCOVA model graphically and will undertake appropriate transformation of the weekly average MME outcome as deemed appropriate. If no suitable transformations can be found, bootstrapped confidence intervals for the between-group differences in weekly MME will be produced. Both adjusted and unadjusted between-group comparisons will be presented with 95% confidence intervals.

---

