#### 10.1.3 CONFIDENTIALITY AND PRIVACY

Participant privacy is strictly held in trust by the participating investigators, their staff, and their interventions. Therefore, the study protocol, documentation, data, and all other information generated will be held in strict confidence. No information concerning the study or the data will be released to any unauthorized third party without prior written approval of the sponsor.

Representatives of the IRB or regulatory agencies may inspect all documents and records required to be maintained by the investigator for the participants in this study. The clinical study site will permit access to such records as needed.

Data in the study is collected in three ways: in real-time, at infrequent intervals throughout the study, and through medical record queries. Real-time data, including biometrics and survey data delivered via mobile device, will be stored on secure servers hosted by Amazon Web Services (AWS) and will contain only a unique identifier for each participant. Virtual reality adherence data will also be tracked in real-time and hosted on secure servers by AppliedVR; a separate unique ID will be assigned to each participant. Data collected at infrequent intervals throughout the study, such as entry, 14-day interval assessments, and exit questionnaires will be stored on secure CSMC servers with unique ID's for each participant. Data collected from medical record numbers, such as opioid prescriptions and physician history, will reside on secure CSMC servers and an ID will be assigned to each individual in order to abstract PHI/PII and the medical record number. Each dataset will utilize different unique ID's and a list linking each unique ID to each participant will be stored internally on the secured CSMC network. The linking list allows a researcher with access to the secured files to merge all data using statistical software, while maintaining data confidentiality.

To minimize risk of breaches in confidentiality associated with the access and recording of protected health information, study staff will be assigned unique passwords and usernames to access secure servers. Additionally, identifiable information for participants will be obfuscated using unique ID numbers and a linking list will be held in a secure location.

A detailed list of procedures that protect confidentiality is in section 20.1 of the MOOP.

---

[figure not shown]

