### *PROMIS-Anxiety*

The change from study baseline to Day 90 in anxiety as measured by *PROMIS-Anxiety* is a secondary endpoint. This analysis will compare the treatment groups, separately, to the control group using a MMRM analysis. The repeated measures are the change from baseline *PROMIS-Anxiety* score obtained at Day 15, 30, 60, and 90, respectively. The model will include fixed categorical effects for treatment, week, treatment by week interaction, and the baseline *PROMIS-Anxiety* score as a continuous covariate. We will employ the Stata *xtmixed* command or the R *lmer* function from the *lme4* package with REML and an unstructured within-patient covariance structure for this model. We will evaluate the assumptions of this model, including normality, using residual and other diagnostic plots of model fit.

From this model, we will estimate least squares means, standard errors, treatment differences in least squares means, and 95% confidence intervals for each time point. Primary inference will be based on the treatment comparison of least squares means for Day 90 from this model, and a p-value will be presented for this time period only. The null hypothesis is that the mean difference in the primary endpoint between the experimental arms and the sham arm is zero, versus the alternative hypothesis that this difference is not zero.

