### *PCS SF-6*

The change from study baseline to Day 90 in pain catastrophizing as measured by PCS SF-6 is a secondary endpoint. This analysis will compare the treatment groups, separately, to the control group using a MMRM analysis. The repeated measures are the change from baseline PCS SF-6 score obtained for Day 15, 30, 60, and 90, respectively. The model will include fixed categorical effects for treatment, week, treatment by week interaction, and the baseline PCS SF-6 score as a continuous covariate. We will employ the Stata *xtmixed* command or the R *lmer* function from the *lme4* package with REML and an unstructured within-patient covariance structure for this model. We will evaluate the assumptions of this model, including normality, using residual and other diagnostic plots of model fit.

From this model, we will estimate least squares means, standard errors, treatment differences in least squares means, and 95% confidence intervals for each time point. Primary inference will be based on the treatment comparison of least squares means for Day 90 from this model, and a p-value will be presented for this time period only. The null hypothesis is that the mean difference in the primary endpoint between the experimental arms and the sham arm is zero, versus the alternative hypothesis that this difference is not zero.

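### The Day 90 models for sleep, anxiety and catastrophizing use four visits, but the schedule marks six post-baseline visits for these scales, and the documents do not explain the difference

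*Protocol*

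**What the plan says.** **Models.** For sleep disturbance, Protocol 9.4.3 and SAP 4.6.2 both take the change from baseline in the "score obtained at Days 15, 30, 60, and 90, respectively". For catastrophizing the Protocol says "The repeated measures are the change from baseline PCS SF-6 score obtained for Day 15, 30, 60, and 90, respectively", and the SAP agrees ("PCS SF-6 score obtained for Day 15, 30, 60, and 90, respectively"). For anxiety only the SAP names visits: "score obtained at Day 15, 30, 60, and 90, respectively". The Protocol's anxiety paragraph points to itself: "The analysis approach for this endpoint mirrors the above description for PROMIS-Anxiety". SAP 4.6.3 (Exploratory Endpoint Analyses) uses the same four days for PROMIS-PF and PROMIS-Depression. All these models have week, treatment by week and an unstructured covariance, and give a p-value at Day 90 only.

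**Schedule.** Protocol 1.3 puts PROMIS Physical Function, Anxiety, Depression and Sleep Disturbance, "Pain intensity/interference with Enjoyment of life/interference with General activity (PEG") and PCS-6 in a single row. That row has one baseline mark and six later marks. The schedule in SAP 3.4 is readable only as a header line, so it cannot settle the point.

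**Other text on frequency.** Protocol 8.2 says PROMIS Depression is completed at baseline and every two weeks. Protocol 10.1.3 mentions "14-day interval assessments, and exit questionnaires". Neither document says why four visits were chosen.

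**The concern.** A repeated-measures model handles dropout under missing at random by using each person's earlier scores to inform the Day 90 mean. A scheduled visit that is left out of the response list cannot help. Two things follow.

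- A late leaver's most recent score may go unused. Day 75 is outside the model on either reading of the schedule, so someone who stops between Days 75 and 90 is represented by Day 60 at the latest.
- If the first modelled visit with data comes after the first collected visits, people who stop in between have post-baseline data but contribute nothing. Protocol 9.3 and SAP 4.2 promise analysis of all randomized patients, and SAP 6.1 relies on the mixed model without further imputation.

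There is also a prespecification problem. If the named visits and the collected visits differ, the analyst must choose the visit list after the data exist, for three secondary and two exploratory endpoints.

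**Working it through.** The plan gives no figure to reproduce here, so the check compares visit lists and then sizes the effect.

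**Step 1: the schedule row.** The header has 12 columns: Pre-screening, Screening, Enrollment, and Days 1, 7, 15, 21, 30, 45, 60, 75 and 90. The row for these scales splits into 12 cells.

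| List | Post-baseline days | Count |
|---|---|---|
| Models | 15, 30, 60, 90 | 4 |
| Schedule row, as the text reads | 7, 21, 30, 60, 75, 90 | 6 |
| Two-weekly reading (my mapping of Protocol 8.2 and 10.1.3 onto the columns) | 15, 30, 45, 60, 75, 90 | 6 |

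- As the text reads: Day 15 is modelled but not scheduled, and Days 7, 21 and 75 are scheduled but not modelled. The models effectively use Days 30, 60 and 90.
- Two-weekly: Days 45 and 75 are scheduled but not modelled, and every modelled visit is scheduled.
- The count does not depend on alignment: 6 - 4 = 2, so at least two scheduled visits are omitted.
- A one-column shift of the whole row does not rescue the models. Shifting right pushes the Day 90 mark off the table, and shifting left pushes off the baseline mark. Only individually misplaced marks could put Day 15 in the row.

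**Step 2: who is affected.** Assume 15-25% missing at Day 90, all of it dropout, spread evenly over the six gaps before each visit. The documents give no dropout pattern.

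- As the text reads, people whose last score is Day 7 or Day 21 fall in two of the six gaps: 15% × 2/6 = 5.0% and 25% × 2/6 = 8.3%. Of 360 that is 18 to 30 people with data who leave the model.
- Two-weekly: none. Day 15 is both the first collected and the first modelled visit.
- On either reading, people whose last score is Day 75 fall in one gap: 15%/6 = 2.5% and 25%/6 = 4.2%, or 9 to 15 of 360. They stay in the model but lose that score.

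**Step 3: effect on the Day 90 standard error.** For dropout pattern k with proportion p_k, let E_k pick out the modelled visits observed and Σ_k be their covariance. The information on the visit means is I = Σ_k p_k E_k′ Σ_k⁻¹ E_k, and the Day 90 variance is the last diagonal element of I⁻¹. The ratio of standard errors (plan's visits over all six) does not depend on sample size or SD. I used compound-symmetric, autoregressive and mixed correlations with values of 0.4 to 0.9.

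| Reading | Visits compared | Increase in SE, even dropout |
|---|---|---|
| Two-weekly | 15, 30, 60, 90 against all six | 0.05% to 0.9% |
| As the text reads | 30, 60, 90 against all six | 0.2% to 4.0% |

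Other dropout mixes over the same ranges reach about 1.5% on the two-weekly reading. In sample-size terms, 1.5% costs 1 - 1/1.015² = 2.9% of the information, and 4% costs 1 - 1/1.04² = 7.5%.

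**Step 4: cost of the larger model.** An unstructured matrix for q visits has q(q+1)/2 parameters: 4×5/2 = 10 for four visits and 6×7/2 = 21 for six.

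**The case against.** The strongest reply is that the Day 15 gap rests on cell positions in a table read from PDF, and other text points the other way. In the same table the baseline mark for these scales falls under Pre-screening, although Protocol 9.4.1 defines baseline as the screening week and the baseline-survey row is marked under Screening. The positions are therefore not reliable. Two-weekly surveys also give exactly six marks, with Day 15 among them. This stands. A reader might infer that Day 15 is never collected, but the documents do not establish that.

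A reader might also infer that early leavers are lost whatever the schedule, contrary to the all-randomized population. That holds only if the marks stand where the text puts them. People with no post-baseline score contribute no response under any visit list.

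Nor are all Day 90 secondary endpoints affected. Opioid dose is analysed by ANCOVA on baseline and Day 90. Pain interference has its own schedule row, marked at every visit, and its own model.

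It is also fair to say that a prespecified subset of visits is a legitimate choice when the only p-value is at Day 90, and that a larger unstructured matrix is harder to estimate. The first would carry more weight if the plan gave a reason and the named visits plainly matched the schedule. The second is minor with 360 patients.

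SAP 6.4 is only a partial answer. Its imputation step is triggered by missingness above 15% in the primary or a key secondary endpoint, and the SAP attaches the label key secondary only to opioid dose. It extends similar considerations to repeated-measures models but does not mention using the omitted visits.

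**Conclusion.** The concern holds as an unexplained mismatch: four modelled visits against six scheduled ones for three secondary and two exploratory scales. That count survives any rearrangement of the marks. Which visits are omitted, and whether anyone leaves the analysis because of it, depends on the source table.

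The numerical effect is small: roughly 0.1-1.5% on the Day 90 standard error if surveys are two-weekly, and up to about 3-4% if the marks are as the text reads. These figures assume correlations of 0.4-0.9, 15-25% missing at Day 90 and monotone dropout. Bias is not quantified, because that would need a dropout mechanism the documents do not give.

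Day 90 is both scheduled and modelled, so the secondary tests remain possible. The gain from a change is a better-supported missing-at-random analysis and a visit list that agrees with the schedule, rather than power. It is a worthwhile, inexpensive correction and not a threat to the trial's conclusions.

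**What to change.** 1. Confirm from the source table, or from the survey system's send dates, when these scales go out.
2. Make Protocol 1.3, 8.2, 9.4.3 and 10.1.3 and SAP 3.4, 4.6.2 and 4.6.3 (Exploratory Endpoint Analyses) state the same days. Replace the Protocol's self-referring anxiety paragraph with an explicit visit list.
3. In the models for sleep disturbance, anxiety, PCS SF-6, PROMIS-PF and PROMIS-Depression, list every scheduled post-baseline visit as a response, with the treatment comparison and p-value still at Day 90.
4. Name in advance a simpler covariance structure to use if the unstructured model does not converge.

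If the team prefers to keep four visits, the SAP should say why and confirm that each is collected. The cost is wording only, since the data are already scheduled. The one statistical price is 21 covariance parameters instead of 10.
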